8.10 USE OF BIOLOGICAL SAMPLES AND DATA FOR FUTURE RESEARCH

Future research may help further the understanding of disease subtypes, disease biology, related conditions, drug response and toxicity, and can help identify new drug targets or biomarkers that predict participant response to treatment. Therefore, data and biological samples will be stored and used for future research when consented to by participants/parent(s)/legally authorized representative (see [Section 10.1.3](#)) unless prohibited by local laws or IRBs/IECs (in such case, consent for future use of sample will not be included in the local ICF).

For participants who consent to the storage and use of their data and remaining and/or extra clinical samples, data and samples may be used after the study ends for future research either to the drug, the mechanism of action, and the disease or its associated conditions. A black rectangular redaction box.

If future research on genetic material is performed, this will also be limited to the purpose of addressing research questions related to the drug, the mechanism of action, the disease or its associated conditions.

In the event future research is conducted for other purposes, the study participants will be informed of those purposes and will be given means to object to those research projects.

Data and samples will be used in compliance with the information provided to participants in the ICF Part 2 (future research).

All study participant data and samples will be coded such that no participant direct identifiers will be linked to them. Coded data and samples may be transferred to a Sponsor site (or a subcontractor site), which may be located outside of the country where the study is conducted. The Sponsor adopts safeguards for protecting participant confidentiality and personal data (see [Section 10.1.4](#)).

The samples will be stored for a maximum of 15 years after the end of the study. Any samples remaining at the end of retention period will be destroyed. If a participant requests destruction of his/her samples before the end of the retention period, the Investigator must notify the Sponsor (or its contract organization) in writing. In such case, samples will be destroyed and related coded data will be anonymized unless otherwise required by applicable laws.

Study participant coded data will be stored for future research for up to 25 years after the end of the study. If data are still considered of important scientific value after this period, coded data already available will be anonymized unless otherwise required by applicable laws (the same will apply to the data of a study participant who has requested the destruction of his/her samples).

[figure not shown]
Participant's coded data sets provided to researchers for a specific research project will be available to the researchers for a maximum of 2 years after the end of their specific project (end of project is defined by publication of the results or finalization of the future research project report).

9 STATISTICAL CONSIDERATIONS

9.1 STATISTICAL HYPOTHESES

The following null and alternative hypotheses will be tested for dupilumab versus placebo:

- H0: No treatment difference between dupilumab and placebo.
- H1: There is a treatment difference between dupilumab and placebo.

9.3 POPULATIONS FOR ANALYSES

The following populations are defined ([Table 6](#)):

Table 6 - Populations for analyses

Population	Description
Screened	All participants who sign the ICF/assent form
Randomized	The randomized population includes all participants with a treatment kit number allocated and recorded in the IRT database, and regardless of whether the treatment kit was used or not. Participants treated without being randomized will not be considered randomized and will not be included in any efficacy population.
Intent-to-treat (ITT)	All randomized participants analyzed according to the treatment group allocated by randomization regardless if treatment kit is used or not.
Safety	All participants randomly assigned to study intervention and who take at least 1 dose of study intervention. Participants will be analyzed according to the intervention they actually received. Randomized participants for whom it is unclear whether they took the study medication will be included in the safety population as randomized. For participants who accidentally receive different treatment from the planned, the actual intervention allocation for as-treated analysis will be the dupilumab group.

Population	Description
Pharmacokinetic (PK)	The PK population includes all participants in the safety population with at least 1 non-missing result for functional dupilumab concentration in serum after first dose of the study treatment. Participants will be analyzed according to the intervention actually received.
Anti-drug antibody (ADA)	ADA population includes all participants in the safety population who have at least 1 non-missing result in the ADA assay after the first dose of the study treatment. Participants will be analyzed according to the intervention actually received.

ADA: antidrug antibody; ICF: informed consent form; IRT: interactive response technology; ITT: intent-to-treat; PK: pharmacokinetic

Endpoints not required for children aged ≥ 6 to < 12 years will be analyzed using the ITT population in adults and adolescents (≥ 12 to < 18 years).

9.4 STATISTICAL ANALYSES

The statistical analysis plan (SAP) will be developed and finalized prior to database lock and will describe the participant populations to be included in the analyses, and procedures for accounting for missing, unused, and spurious data. This section is a summary of the planned statistical analyses of the most important endpoints including the primary and secondary endpoints.

9.4.1 General considerations

All comparisons will be of dupilumab (300 mg q2w and 300 mg q4w and 200 mg q2w) versus placebo.

The baseline value is defined generally as the last available value before randomization. For endpoints collected on the daily Nasal Symptom Diary, baseline is defined as the average of the scores in the 7 days prior to randomization.

For efficacy analyses, a multiplicity-controlled hierarchical testing is proposed to control the overall type-I error rate for testing the primary and select secondary efficacy endpoints at an alpha of 0.05. The detailed hierarchical testing procedure will be defined in the study SAP. The study is considered positive when the primary endpoint achieves statistical significance with 2-sided significance level 0.05.

Data collected regarding the impact of the COVID-19 or other pandemics on the participants will be summarized (eg, discontinuation due to COVID-19). Any additional analyses and methods required to investigate the impact of COVID-19 or other pandemics pandemic requiring public health emergency on the efficacy (eg, missing data due to COVID-19) and safety will be detailed in the SAP.

9.4.2 Primary endpoint(s)

The primary estimand for the primary endpoint of change from baseline in LMK score at Week 52 is the composite/treatment policy strategy, as described in [Table 7](#).

Table 7 - Summary of primary estimand for the primary endpoint

Endpoint Category	Estimands			
	Endpoints	Population	Intercurrent event(s) handling strategy and missing data handling	Population-level summary
Objective: To evaluate the efficacy of treatment with dupilumab to reduce sinus opacification in a population with allergic fungal rhinosinusitis (AFRS)				
Primary endpoint	Change from baseline in LMK score at Week 52	ITT	
The following intercurrent events will be handled with a composite strategy; data after the IE will be excluded and the worst post-baseline value on or before the start of the IE will be assigned to the Week 52 value (WOCF); for participants with no post-baseline values, the baseline value will be used.
 
 Undergo/plan to undergo surgery for AFRS prior to Week 52 Taking SCS for any reason prior to Week 52 Starting prohibited biologics prior to Week 52 
The following IEs will be handled with the treatment policy strategy (without IEs that need to be handled with composite strategy). All assessments after starting such IE will be included.
 
 Discontinuing the study intervention Taking antifungals or other prohibited/rescue medications 
In addition, the missing data imputation rules are as follows:
 
 For missing data, a multiple imputation approach will be used to impute missing Week 52 values, and this multiple imputation will use all data from participants excluding participants who undergo/plan to undergo surgery for AFRS on or before Week 52. 	ANCOVA model with intervention group, time from last surgery (≤ 2 years, > 2 years), region (countries combined), and relevant baseline measurement as covariates is used. Statistical inference obtained from all imputed data by ANCOVA model will be combined using Rubin's rule.

The primary endpoint of change from baseline in LMK score at Week 52, will be analyzed using an analysis of covariance (ANCOVA) model with the baseline LMK score, intervention group, time from last surgery (≤ 2 years, > 2 years) and region (combined countries) as covariates, with intercurrent events and missing data being handled by a hybrid method of the worst-observation carried forward (WOCF) and multiple imputation. For participants who undergo/plan to undergo surgery for AFRS, take SCS for any reason or start prohibited biologics, data collected after these IEs will be excluded from analysis and the worst post-baseline value on or before the IE will be assigned to the Week 52 value (ie, WOCF approach). For participants with no post-baseline values, the baseline value will be used (composite strategy). Participants who discontinue the

study intervention prematurely are encouraged to follow the planned clinical visits and, in these participants (if without or before the IEs that need to be handled with composite strategy), all data collected after study intervention discontinuation will be included in the analysis (treatment policy strategy). In case there is missing data, a multiple imputation approach will be used to impute missing Week 52 values, and this multiple imputation will use all participants excluding participants who undergo/plan to undergo surgery for AFRS, take SCS for any reason or start prohibited biologics on or before Week 52. Each of the imputed complete data will be analyzed by fitting an ANCOVA model with the baseline covariate and factors for intervention group, time from last surgery (≤ 2 years, > 2 years), and region (combined countries). Statistical inference obtained from all imputed data will be combined using Rubin's rule. Descriptive statistics including number of participants mean, standard error, and LS means will be provided. In addition, difference in LS means and the corresponding 95% CI will be provided along with the p-values.

Subgroup analyses

To assess the consistency in treatment effects across different subgroup levels, subgroup analyses will be performed for the primary efficacy endpoint with respect to age group, gender, region, and other factors that will be specified in the SAP.

9.4.3 Secondary endpoint(s)

Statistical analysis methods for the secondary efficacy endpoints listed in [Table 1](#) are presented below.

The primary estimand for the secondary endpoint of proportion of participants who receive SCS and/or undergo/plan to undergo surgery for AFRS during the 52-week treatment period is the *treatment policy/while before rescue strategy*, as described in [Table 8](#).

Table 8 - Summary of primary estimand for the proportion secondary endpoint

Endpoint Category	Estimands			
	Endpoints	Population	Intercurrent event(s) handling strategy and missing data handling	Population-level summary
Secondary objective: To assess the efficacy of dupilumab to reduce the need for rescue treatments				
Secondary endpoint	Proportion of participants who receive SCS and/or undergo/plan to undergo surgery for AFRS during the 52-week treatment period.	ITT	
The following IEs will be handled with a treatment policy strategy (if without/before taking prohibited biologics):
 
 • Discontinuation of study intervention • Taking antifungals or other prohibited/rescue medications 
The following IE will be handled with a while before rescue strategy, All data before starting prohibited biologics will be included in the analysis.
 
 • Starting prohibited biologics 
In addition, the missing data imputation rules are as follows:
 
 • Discontinuing the study follow-up without an event prior to discontinuation: Participant will be considered as no event. 	Cochran-Mantel-Haenszel (CMH) test stratifying by time from last surgery (≤ 2 years, > 2 years), and region (combined countries). The estimate of the odds ratio between dupilumab and placebo will be derived.

This secondary endpoint will be analyzed using a CMH test stratifying by time from last surgery (≤ 2 years, > 2 years) and region (combined countries). All data collected after study intervention discontinuation and before starting prohibited biologics will be included in the analysis. Participants who discontinue the study follow-up without an event will be considered as no event. The estimate of the odds ratio between dupilumab and placebo will be derived with the corresponding 95% CI and p-value.

The change from baseline to Week 24 and Week 52 in the continuous secondary endpoints will be analyzed using the same analysis approach as for the primary endpoint of change from baseline in LMK score at Week 52.

9.4.5 Other safety analyses

All safety analyses will be performed on the safety population. The summary of safety results will be presented by treatment group. The baseline value is defined generally as the last available value before first dose of IMP.

Adverse event incidence tables will present by system organ class (SOC) (sorted by internationally agreed order) and preferred term (PT), the number (n) and percentage (%) of participants experiencing an AE. Multiple occurrences of the same event in the same participant will be counted only once in the tables within a treatment phase. The denominator for computation of percentages is the safety population within each treatment group.

Proportion of participants with at least 1 treatment-emergent adverse event (TEAE), treatment-emergent SAE, TEAE leading to death, and TEAE leading to permanent treatment discontinuation will be tabulated by treatment group. In addition, TEAEs will be described according to maximum intensity and relation to the study intervention. Serious AEs and AEs leading to study discontinuation that occur outside the treatment-emergent period will be summarized separately.

Incidence of each type of AESI and other AE groupings will be tabulated by treatment group. For each type of AESI, the following analysis will be generated.

A summary of the number (%) of participants with

- Any TEAE.
- Any SAE (regardless of treatment-emergent status).
- Any treatment-emergent SAE.
- Any AE leading to death.
- Any TEAE leading permanent treatment discontinuation.
- Any TEAE related to study intervention reported by the Investigator.
- Any TEAE by maximum intensity, corrective treatment, and final outcome.

The method to identify AESIs and other AE groupings will be specified in the SAP.

The following deaths summaries will be generated:

- Number (%) of participants who died by study period (TEAE, on-study) summarized on the safety population by treatment received.
- Death in nonrandomized participants or randomized and not treated participants.
- TEAE leading to death (death as an outcome on the AE eCRF page as reported by the Investigator) by primary SOC and PT showing number (%) of participants.

Results and change from baseline for the laboratory parameters will be summarized by treatment group for baseline and each post baseline time point, endpoint, minimum and maximum value. Summary statistics will include number of participants, mean, standard deviation, median, Q1, Q3, minimum, and maximum.

The following definitions will be applied to laboratory parameters.

- The potentially clinically significant abnormality (PCSA) values are defined as abnormal values considered medically important by the Sponsor according to predefined criteria/thresholds based on literature review and defined by the Sponsor for clinical laboratory tests.

- PCSA criteria will determine which participants had at least 1 PCSA during the on-treatment period, taking into account all evaluations performed during the on-treatment period, including unscheduled or repeated evaluations. The number of all such participants will be the numerator for the on-treatment PCSA percentage.

The proportion of participants who had at least 1 incidence of PCSA at any time during the treatment-emergent period will be summarized by treatment group. Shift tables showing changes with respect to the baseline status will be provided.

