1.3 SCHEDULE OF ACTIVITIES (SOA)

Procedure	Screening 2-4 wks D-28 to D-14	Intervention period weeks						Follow-up (Wk 64, 12 weeks after EOT)/EOS ^c	Notes
		Wk 0 D1 ^a	Wk 2 D15 ^x	Wk 12 D85	Wk 24 D169	Wk 36 D252	Wk 52 D364 EOT ^b		
Visit	1	2	3	4	5	6	7	8	Visit window: +3 days for Visit 2, ±3 days for Visits 3 to 7, ±5 days for Visit 8
Screening and baseline									
Informed consent/assent ^d	X								
Inclusion and exclusion criteria	X	X							Recheck clinical status before randomization.
Participant demography	X								
Full physical examination	X	X			X		X		Including skin (full body skin exam), nasal cavities, eyes, ears, respiratory, cardiovascular, gastrointestinal, neurological, lymphatic, and musculoskeletal systems.
Medical/surgical history ^e	X								
Record planned endoscopic sinus surgery ^f	←————→								
Prior/Concomitant medications	X	X	X	X	X	X	X	X	Check INCS as prior medication at screening and background medication during study period. Record rescue therapy, if applicable.
Randomization		X							
Log-in to IRT	X	X	X	X	X	X	X	X	

Procedure	Screening 2-4 wks D-28 to D-14	Intervention period weeks						Follow-up (Wk 64, 12 weeks after EOT)/EOS ^c	Notes
		Wk 0 D1 ^a	Wk 2 D15 ^x	Wk 12 D85	Wk 24 D169	Wk 36 D252	Wk 52 D364 EOT ^b		
Visit	1	2	3	4	5	6	7	8	Visit window: +3 days for Visit 2, ±3 days for Visits 3 to 7, ±5 days for Visit 8
Study intervention^g									
IMP administration ^h									IMP will be administered every 14 ±3 days (q2w) for participant weighing ≥30 kg (measured at screening) or 28±3 days (q4w) for participant weighing <30 kg (measured at screening). Between visits at site, home administration is allowed after appropriate training of the participant (or parent/legally authorized representative, or caregiver). The planned last dose is at Week 50 for q2w injections and Week 48 for q4w injections.
Efficacy assessmentsⁱ									
Nasal Endoscopy ⁱ	X	X		X	X	X	X	X	For participant aged ≥6 to <12 years old, nasal endoscopy will only be mandatory at screening, Week 0, Week 24, and Week 52.
CT scan ^k	X				X		X		Initial CT scan to be done during screening period results should be available prior to randomization (Visit 2). Week 24 CT scan is not required for adolescents/children.

Procedure	Screening 2-4 wks D-28 to D-14	Intervention period weeks						Follow-up (Wk 64, 12 weeks after EOT)/EOS ^c	Notes
		Wk 0 D1 ^a	Wk 2 D15 ^x	Wk 12 D85	Wk 24 D169	Wk 36 D252	Wk 52 D364 EOT ^b		

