6.1 STUDY INTERVENTION(S) ADMINISTERED

Table 2 - Overview of study interventions administered

ARM name	Dupilumab	Placebo
Intervention name	Dupilumab 200 mg or Dupilumab 300 mg	Placebo
Type	Biological	Other
Dose formulation	Dupilumab 200 mg: A 175 mg/mL dupilumab solution in a pre-filled syringe to deliver 200 mg in 1.14 mL. or Dupilumab 300 mg: A 150 mg/mL dupilumab solution in a pre-filled syringe to deliver 300 mg in 2 mL.	Placebo matching dupilumab 200 mg will be supplied as an identical formulation to the active 200 mg formulation without dupilumab, in a pre-filled syringe to deliver placebo in 1.14 mL. or Placebo matching dupilumab 300 mg will be supplied as an identical formulation to the active 300 mg formulation without dupilumab, in a pre-filled syringe to deliver placebo in 2 mL.
Unit dose strength(s)	200 mg or 300 mg	0 mg
Dosage level(s)	One injection of 200 mg q2w for adolescents/children \geq 30 kg and <60 kg at screening or One injection of 300 mg q2w for all adults and for adolescents/children weighing \geq 60 kg at screening or One injection of 300 mg q4w for adolescents/children \geq 15 kg and <30 kg at screening	One injection of placebo matching 200 mg q2w for adolescents/children \geq 30 kg and <60 kg at screening or One injection of placebo matching 300 mg q2w for all adult participants and for adolescents/children weighing \geq 60 kg at screening or One injection of placebo matching 300 mg q4w for adolescents/children \geq 15 kg and <30 kg at screening
Route of administration	Subcutaneous injection	Subcutaneous injection
Use	Experimental	Experimental
IMP	IMP	IMP
Packaging and labeling	Each dose of dupilumab will be supplied as 1 glass pre-filled syringe packed in a participant kit box. Both glass pre-filled syringe and box will be labeled as required per country requirement	Each dose of placebo will be supplied as 1 glass pre-filled syringe packed in a participant kit box. Both glass pre-filled syringe and box will be labeled as required per country requirement

The IMP will be administered every 14 ± 3 days (q2w) or 28 ± 3 days (q4w) during the 52-week treatment period (with the last IMP administration at Week 50 for q2w administrations and at Week 48 for q4w administrations).

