- The **treatment-emergent (TE) period** is defined as the period from the first IMP administration to the last IMP administration +98 days. The treatment-emergent period includes the following 2 periods:

- The **on-treatment period** is defined as the period from the first IMP administration to the last administration of the IMP +14 days for adults and adolescents/children ≥ 30 kg at screening or 28 days for adolescents/children ≥ 15 kg and < 30 kg at screening.
- The **residual treatment period** is defined as the period from the end of the on-treatment period to the end of the treatment-emergent period.
- The **post-treatment period** is defined as the period from the end of the treatment-emergent period.

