3.6 SAFETY ANALYSES

All safety analyses will be performed on the safety population as defined in [Section 2](#), unless otherwise specified, using the following common rules:

- The analysis of the safety variables will be essentially descriptive, and no testing is planned.
- Safety data in participants who do not belong to the safety population (eg, exposed but not randomized) will be provided separately.

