3.6.2 Adverse events

General common rules for adverse events

All adverse events (AEs) will be coded to a lower-level term (LLT), preferred term (PT), high-level term (HLT), high-level group term (HLGT), and associated primary system organ class (SOC) using the Medical Dictionary for Regulatory Activities (MedDRA) version currently in effect at Sanofi at the time of database lock.

The AEs will be analyzed in the following 3 categories:

- Pre-treatment AEs: AEs that developed, worsened or became serious during the pre-treatment period.
- Treatment-emergent adverse events (TEAE)s: AEs that developed, worsened or became serious during the treatment-emergent period.
- Post-treatment AEs: AEs that developed, worsened or became serious during the post-treatment period.

Similarly, the deaths will be analyzed in the pre-treatment, treatment-emergent and post-treatment periods.

The primary AE analyses will be on TEAEs. Pre-treatment and post-treatment AEs will be described separately.

An AE with incomplete or missing date/time of onset (occurrence, worsening, or becoming serious) will be classified as a TEAE unless there is definitive information to determine it is a pre-treatment or a post-treatment AE.

If the assessment of the relationship to IMP is missing for an AE, this AE will be assumed as related to IMP. Missing severity will be left as missing.

Multiple occurrences of the same event in the same participant will be counted only once in the tables within a treatment phase.

The AE tables will be sorted as indicated in [Table 4](#).

Table 4 - Sorting of AE tables

AE presentation	Sorting rules
SOC, HLGT, HLT and PT	By the internationally agreed SOC order and by alphabetic order of HLGTs, HLTs and PTs.
SOC, HLT and PT	By the internationally agreed SOC order and by alphabetic order of HLTs and PTs.
SOC and PT	By the internationally agreed SOC order and decreasing frequency of PTs ^{a,b}
SMQ/CMQ and PT	By decreasing frequency of SMQs/CMQs and PTs ^a
PT	By decreasing frequency of PTs ^a

^a Sorting will be based on the dupilumab intervention group.

^b The table of all TEAEs presented by primary SOC and PT will define the presentation order for all other tables (eg, treatment-emergent SAE) presented by SOC and PT, unless otherwise specified.

Analysis of all adverse events

The overview of TEAE with the details below will be generated:

- Any TEAE
- Any severe TEAE

- Any treatment-emergent SAE
- TEAE leading to death

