- Any TEAE leading to permanent intervention discontinuation
- Any treatment-emergent AESI
- Any treatment-emergent other AE of interest grouping
- Any TEAE related to IMP

The AE summaries of **Table 5** will be generated with number (%) of participants experiencing at least one event. A separate analysis of TEAE by primary SOC and PT will be provided for pediatric patients.

Table 5 - Analyses of adverse events

Type of AE	MedDRA levels
All TEAE	Primary SOC, HLGT, HLT and PT
	Primary SOC and PT
	Primary SOC
	PT
Common TEAE ($\geq 5\%$ in any group)	Primary SOC and PT
TEAE related to IMP as per Investigator's judgment	Primary SOC, HLGT, HLT and PT
	Primary SOC and PT
TEAE by maximal intensity	Primary SOC and PT
Treatment emergent SAE	Primary SOC, HLGT, HLT and PT
	Primary SOC and PT
Treatment emergent SAE related to IMP as per Investigator's judgment	Primary SOC and PT
TEAE leading to permanent intervention discontinuation	Primary SOC, HLGT, HLT and PT
	Primary SOC and PT
TEAE leading to death ^b	Primary SOC, HLGT, HLT and PT
	Primary SOC and PT
Pretreatment AE	Overview ^a
	Primary SOC and PT
Post-treatment AE	Overview ^a
	Primary SOC and PT
Post-treatment SAE	Primary SOC and PT

^a Will include the following AE categories: any AEs, any serious AEs, any AEs leading to death, any AEs leading to permanent intervention discontinuation

^b Death as an outcome of the AE as reported by the Investigator in the AE page

Analysis of deaths

In addition to the analyses of deaths included in Table 5 the number (%) of participants in the following categories will be provided:

- Deaths during the treatment-emergent and post-treatment periods by main reason for death
- Deaths in non-randomized participants or randomized but not treated participants

Analysis of adverse events of special interest (AESIs) and other AEs of interest

Adverse events of special interest (AESIs) and other AEs of interest will be selected for analyses as indicated in [Table 6](#). Number (%) of participants experiencing at least one event will be provided for each event of interest, by PT if applicable. Tables will be sorted as indicated in [Table 4](#).

Table 6 - Selections for AESIs and other AEs of interest

AESIs and other AEs of interest	Selection
AESI	

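### Post-treatment AE and SAE percentages are taken over the whole safety population, yet q2w completers have almost no post-treatment time, so the arm figures mainly track who stopped IMP early and stayed in follow-up

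*Protocol*

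**What the plan says.** - **Denominator.** Protocol 9.4.5 says of the AE incidence tables: "The denominator for computation of percentages is the safety population within each treatment group". The sentence before it counts repeated events once per treatment phase, so the rule is not confined to TEAEs. SAP 3.6 agrees: "All safety analyses will be performed on the safety population as defined in" Section 2, unless otherwise specified. Nothing else is specified for post-treatment events.
- **Statistic.** SAP 3.6.2 says the summaries in Table 5 "will be generated with number (%) of participants experiencing at least one event". Table 5 has post-treatment AE rows (an overview, and SOC/PT) and a post-treatment SAE row.
- **Periods.** SAP 3.1: the treatment-emergent period "is defined as the period from the first IMP administration to the last IMP administration +98 days", and the post-treatment period "is defined as the period from the end of the treatment-emergent period". SAP 3.6.2 defines post-treatment AEs as "AEs that developed, worsened or became serious during the post-treatment period".
- **Schedule.** Protocol 6.1 describes a 52-week treatment period "with the last IMP administration at Week 50 for q2w administrations and at Week 48 for q4w administrations". The last visit in the Schedule of Activities is "Follow-up (Wk 64, 12 weeks after EOT)/EOS", with a window of ±5 days. SAP Table 7 places it at Day 448.
- **After early stopping.** Protocol 7.1.1 follows participants to the scheduled study completion date. Protocol 4.4 counts someone who stops before Week 40 and is followed to Week 52 as having completed the study.
- **Exposure adjustment.** SAP 3.6.2 provides rates per 100 participant-years if treatment exposure is imbalanced, for treatment-emergent summaries only.

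**The concern.** A percentage of the safety population can be compared between arms when everyone in it has a similar opportunity to have the event. In the post-treatment rows that is not so. The 98-day tail uses up practically all scheduled follow-up of a q2w completer, while an early stopper kept in the study can accrue weeks to months. Most of each denominator can hardly contribute an event, and the numerator depends on how many participants in that arm stopped IMP early and were still followed more than 98 days later.

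That number could well differ by arm. Protocol 7.1.1 makes sino-nasal surgery a reason for ending IMP, and one aim of the trial is to show that dupilumab reduces the need for surgery. If it does, more placebo participants may reach the post-treatment period, and placebo would show more post-treatment AEs without any difference in event rate. What is at stake is the reading of these tables in the study report, not an efficacy conclusion.

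**Working it through.** **1. The 98 days against the schedule.** Week 64 − Week 50 = 14 weeks = 98 days, so for q2w dosing the treatment-emergent period ends at the nominal final visit.

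**2. Post-treatment days for completers.** Day of last dose = 1 + 7 × week. Post-treatment days = max(0, final-visit day − (last-dose day + 98)). The final visit is Day 448 ±5, that is Days 443-453.

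- q2w: 1 + 7×50 = 351; 351 + 98 = 449; 0 days at the target visit, at most 453 − 449 = 4.
- q4w: 1 + 7×48 = 337; 337 + 98 = 435; from 443 − 435 = 8 to 453 − 435 = 18.
- If Week 64 is Day 449, as in SAP Table 8, the q2w maximum is 5. A last dose 3 days early raises the maximum from 4 to 7, and a late end-of-treatment visit as well raises it to 10.

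**3. Post-treatment days for early stoppers.**

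| Last dose | Period starts (day) | To Week 52 (Day 364) | To Week 64 (Day 448) |
|---|---|---|---|
| Week 12 | 183 | 181 | 265 |
| Week 24 | 267 | 97 | 181 |
| Week 36 | 351 | 13 | 97 |
| Week 44 | 407 | 0 | 41 |

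**4. Effect on the percentages.** The documents give no stopping rates or AE rates, so these inputs are assumptions: 31 per arm, 6 stoppers in one arm and 2 in the other, all at Week 12, a constant 1.5 AEs per year in both arms, completers with 0 days. Risk for a stopper = 1 − exp(−1.5 × days/365.25).

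- To Week 52: 1 − exp(−1.5×181/365.25) = 0.524. Table: 6×0.524/31 = 10.2% v 2×0.524/31 = 3.4%.
- To Week 64: 1 − exp(−1.5×265/365.25) = 0.663. Table: 12.8% v 4.3%.

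Other inputs: 8 v 2 stoppers at Week 24 followed to Day 448 give 5.7% v 1.4%, 10.1% v 2.5% and 16.2% v 4.1% at 0.5, 1 and 2 AEs per year. The gap is fourfold throughout, the same as the ratio of stoppers.

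**5. Share of person-time held by Week 12 stoppers.** It is lowest with 2 stoppers followed to Week 52 and every completer at 4 days: 2×181/(2×181 + 29×4) = 362/478 = 76%. With final visits spread evenly over Days 443-453, completers average (1+2+3+4)/11 = 0.91 days. With 6 stoppers followed to Week 64 the share is then 1590/(1590 + 25×0.91) = 99%.

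**6. Would a new percentage denominator suffice?** Take as denominator everyone followed beyond last dose +98 days, with the inputs of step 4 but final visits spread evenly. Then 4 of the 11 possible visit days (450-453) bring a completer in. The denominators are 6 + 25×4/11 = 15.1 and 2 + 29×4/11 = 12.5. A completer's average risk is about 0.0037.

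- To Week 52: (6×0.524 + 25×0.0037)/15.1 = 21% v (2×0.524 + 29×0.0037)/12.5 = 9%.
- To Week 64: 27% v 11%.

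The gap remains.

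**7. Would a rate suffice?** With time censored at the first event, expected time per participant is risk/1.5 years. Stoppers to Week 52: 3.15 cases in 2.10 years and 1.05 cases in 0.70 years, both 150 per 100 participant-years. Completers' short follow-up adds cases and time in the same proportion, so the rates stay equal.

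**The case against.** The best defence is that these rows are residual reporting. SAP 3.6.2 makes TEAEs the primary AE analysis and describes post-treatment AEs separately; SAP 3.6 plans no safety testing. Early stopping will be visible in the disposition and exposure tables, and Protocol 7.1.1 expects definitive discontinuation to be rare. A uniform safety-population denominator is a common convention. All of this stands and limits the weight of the point. It does not make the two percentages comparable, and no planned table shows the post-treatment time behind them.

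Four stronger readings go beyond the documents:

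- **That the figures reflect early stopping as such.** Stoppers who leave the study, or who stop late and are followed only to Week 52, add little or nothing. The driver is early stopping together with follow-up past last dose +98 days.
- **That the true risk is understated.** A percentage of the safety population is a different quantity from risk among those still observed. The fault lies in comparing the arms.
- **That restricting the denominator would show equal risk in both arms.** That holds only if no completer has any post-treatment time (working, step 6).
- **That the post-treatment row for AEs leading to permanent discontinuation must be empty.** The SAP definition includes AEs that worsen or become serious in that period. An AE that led to stopping IMP and worsened later belongs there.

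**Conclusion.** The point holds as a minor one. For on-schedule q2w dosing, the SAP's 98-day window leaves completers 0-4 days of post-treatment time, against 181-265 days for a Week 12 stopper kept in follow-up. The by-arm percentages therefore depend mainly on how many such participants each arm has. Under the assumed 6 v 2 split at equal event rates, the tables would show about a threefold difference (10.2% v 3.4%, or 12.8% v 4.3%), with stoppers holding roughly 76-99% of an arm's post-treatment person-time, depending on when completers attend the final visit. The day counts follow from the documents; the percentages rest on assumed stopping patterns and AE rates. Later stopping or more balanced arms would shrink the difference. No planned test, and no part of the primary AE analysis, is affected.

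**What to change.** In SAP 3.6.2, for the post-treatment AE and SAE rows of Table 5, show per arm:

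- the number of participants with follow-up beyond last IMP +98 days;
- their post-treatment participant-time;
- participants with at least one event per 100 participant-years, with time censored at the first event. This extends the method that the section already uses for treatment-emergent summaries.

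The existing percentages can stay beside these figures. Keep the row for AEs leading to permanent intervention discontinuation.

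The cost is one added SAP statement and extra columns in the affected tables, with no new data or visits. The drawback is that the rates will rest on little person-time and be imprecise; showing the participant-time makes that visible.
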